### **3.2. Discussion of Study Design, Including the Choice of Control Groups**

This study will be double-blind and placebo-controlled to avoid bias in the collection and evaluation of data during its conduct. The Sponsor will remain blinded to the treatment

randomization code until after the database has locked. The Sponsor will perform ongoing review of blinded data. The placebo has been chosen as the control treatment to assess whether any observed effects are treatment-related or simply reflect the study conditions.

### **3.3. End of Study Definition**

The end of the study is defined as the date of the last visit of the last patient in the study.

### **3.4. Selection of Doses in the Study**

Dalcetrapib is already in clinical development (NCT02525939), and of 11,799 subjects that have been dosed to date, a total of 546 subjects have received single oral doses of between 100 and 4500 mg and 467 subjects have received consecutive doses between 300 and 3900 mg. Available information at higher doses showed systemic exposure of 1.73-2.68, 4.30, 3.78, 3.26, 5.63, and 7.11  $\mu\text{g}/\text{mL}$  (maximum concentration [ $C_{\max}$ ]) and 18.2-19.1, 31.3, 30.4, 25.3, 42.3, and 51.1  $\mu\text{g} \cdot \text{h}/\text{mL}$  (area under the concentration-time curve during 24 hours [ $\text{AUC}_{0-24}$ ]) at 900, 1200, 1800, 2100, 3000, and 3900 mg, respectively. In vitro testing showed a protease inhibition  $\text{IC}_{50}$  value of 14.4  $\mu\text{M}$  and inhibition of replication  $\text{IC}_{50}$  value of 17.8  $\mu\text{M}$ . Proposed oral dose levels of dalcetrapib at 900, 1800, or 3600 mg for 10 days is centered on the following:

- 900 mg: based on actual  $C_{\max}$  values of 1.73-2.68  $\mu\text{g}/\text{mL}$  = 5.4-8.37  $\mu\text{M}$  which are 2.7-1.7- and 3.3-2.1-fold lower than protease inhibition and inhibition of replication  $\text{IC}_{50}$  values, respectively to establish whether that this is not an efficacious dose.
- 1800 mg: based on actual  $C_{\max}$  value of 3.78  $\mu\text{g}/\text{mL}$  = 11.8  $\mu\text{M}$  which is approximately 0.8-fold and 0.65-fold the values for protease inhibition and inhibition of replication  $\text{IC}_{50}$  values, respectively, to establish whether this is an efficacious dose.
- 3600 mg: based on actual  $C_{\max}$  values for the 3000 and 3900 mg doses of 5.63 and 7.10  $\mu\text{g}/\text{mL}$  = 17.6 and 22.2  $\mu\text{M}$  which are at or higher the values for protease inhibition and inhibition of replication  $\text{IC}_{50}$  values, respectively, to establish whether this is an efficacious dose.

## 4. SELECTION OF STUDY POPULATION

Prospective approval of protocol deviations to recruitment and enrollment criteria, also known as protocol waivers or exemptions, is not permitted.

### 4.1. Inclusion Criteria

Patients must satisfy all of the following criteria unless otherwise stated:

1. Willing and able to provide informed consent
2. Male or female patients > 18 years of age on the day of informed consent
3. Have received a confirmed diagnosis of COVID-19 (positive for SARS-CoV-2), as assessed by PCR or point-of-care within 72 hours of first dose on Day 1
4. Have mild to moderate signs or symptoms of COVID-19 with onset within 5 days of first dose on Day 1, at least two of the following symptoms:
  - stuffy or runny nose
  - sore throat
  - shortness of breath
  - cough
  - fatigue
  - myalgia
  - headache
  - chills or shivering
  - feeling hot or feverish
  - nausea
  - vomiting
  - diarrhea
  - anosmia
  - ageusia
5. Outpatient with COVID-19 disease (not requiring oxygen therapy [WHO COVID-19 Clinical Improvement Ordinal Scale, score of 3])
6. Patient is aware of the investigational nature of this study and willing to comply with protocol treatments, blood tests, and other evaluations listed in the ICF.

### 4.2. Exclusion Criteria

Patients will be excluded from the study if they satisfy any of the following criteria unless otherwise stated:

1. Females who are pregnant (negative pregnancy test required for all women of child-bearing potential at Screening) or breast-feeding
2. Male patients and women of childbearing potential (women who are not surgically sterile or postmenopausal defined as amenorrhea for >12 months) who are not using at least one protocol-specified method of contraception

3. Severe COVID-19 disease as defined by the WHO COVID-19 Clinical Improvement Ordinal Scale, scores of 5 (non-invasive ventilation or high-flow oxygen), 6 (intubation and mechanical ventilation), or 7 (ventilation + additional organ support pressors, renal replacement therapy [RRT], extracorporeal membrane oxygenation [ECMO])
4. Expected survival less than 72 hours
5. Peripheral capillary oxygen saturation (SpO2) <90% while breathing room air
6. Treatment with other drugs thought to possibly have activity against SARS-CoV-2 infection like remdesivir, favipiravir, within 7 days prior to enrollment or concurrently
7. History of abuse of drugs or alcohol that could interfere with adherence to study requirements as judged by the Investigator
8. Use of any other concurrent investigational drugs while participating in the present study
9. Patient requires frequent or prolonged use of systemic corticosteroids ( $\geq 20$  mg of prednisone/day or equivalent for  $>4$  weeks) or other immunosuppressive drugs (e.g., for organ transplantation or autoimmune conditions)
10. Known renal disease with an estimated glomerular filtration rate (eGFR) <50 mL/min based on local laboratory results
11. Patients with clinically apparent liver disease, e.g., jaundice, cholestasis, hepatic synthetic impairment, or active hepatitis
12. Alanine transaminase (ALT) or aspartate transaminase (AST)  $>3 \times$  upper limit of normal (ULN) or alkaline phosphatase or bilirubin levels  $> 2 \times$  ULN based on local laboratory results
13. Co-administration of clinical doses of orlistat with dalcetrapib
14. Inability to swallow oral medications or a gastrointestinal disorder with diarrhea (e.g., Crohn's disease) or malabsorption at Screening
15. Any other clinically significant medical condition or laboratory abnormality that, in the opinion of the Investigator, would jeopardize the safety of the patient or potentially impact patient compliance or the safety/efficacy observations in the study
16. History of an allergic reaction or hypersensitivity to the study drug or any component of the study drug formulation.

#### **4.3. Disease Diagnostic Criteria**

Patients with SARS-CoV-2 infection confirmed (nasal, nasopharyngeal, oropharyngeal, or respiratory samples, not serology testing, or patients with pre-study confirmed PCR test) and mild to moderate symptoms related to COVID-19 disease are required for enrollment.

The entry testing is performed locally based on testing methods available at the site, such as PCR or rapid antigen test, to confirm the presence of SARS-CoV-2 in a person with symptoms compatible with COVID-19. Both saliva (Oragene) collection and self-collection of mid-turbinate nasal swab under supervision of a healthcare professional (virtual or home visit) will also occur at Screening/Baseline, Day 1, Day 3, Day 5, Day 7, Day 10, and Day 28.

## **4.4. Discontinuation Criteria**

### **4.4.1. Screen Failures**

Screen failures are defined as patients who have provided informed consent to participate in the clinical study but are not subsequently enrolled in the study. A minimal set of screen failure information is required to ensure transparent reporting of screen failure patients to meet the Consolidated Standards of Reporting Trials publishing requirements and to respond to queries from regulatory authorities. Minimal information includes demography, screen failure details, eligibility criteria, and any serious adverse events (SAEs).

Re-screening will be allowed in a screen failed patient if there is a change in the situation of the patient which allows him/her to fulfill inclusion/exclusion criteria with the permission from the Medical Monitor.

### **4.4.2. Discontinuation of Study Treatment**

Study medication will be discontinued for the following reasons:

- Patients whose screening labs indicate an eGFR <50mL/min using CKD-EPI will discontinue study medication and be followed for safety
- Withdrawal by patient (patient is free to discontinue at any point of time; specify reason of discontinuation in the eCRF)
- At the discretion of the Investigator for safety, behavioral, or administrative reasons
- Lack of efficacy (e.g., patients who require nonstudy antiviral or anticytokine therapy due to progression of COVID-19). Note: Study medication would be discontinued upon worsening of symptoms requiring hospitalization, in such cases patients could receive remdesivir
- Adverse event

Study will be discontinued for the following reasons:

- Withdrawal of consent (patient is free to discontinue at any point of time; specify reason of discontinuation in the eCRF)
- Sponsor determination
- Unexpected safety concerns
- Medical or ethical reasons affecting the continued performance of the study
- Difficulties in the recruitment of patients

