### **5.5. Treatment Compliance**

Records shall be maintained of the delivery of study treatment to the study sites, the inventory at the study sites, the use for each patient, and the return to the Sponsor.

These records shall include dates, quantities, batch/lot information, expiry dates, and the unique code numbers assigned to the study treatment and study patients.

---

The Investigator shall be responsible for ensuring that the records adequately document that the patients were provided the doses specified in the protocol and that all study treatment received from the Sponsor is reconciled.

Site staff will monitor compliance of patients with their assigned randomized treatment (dalcetrapib 900, 1800, or 3600 mg or placebo) by recording the number of tablets actually used.

For patients who are hospitalized, patients will be administered treatment by the site staff during hospitalization. On discharge, all patients are to be reminded of the importance of compliance with the treatment with an emphasis on taking their study treatment on schedule and contacting the study site for an appointment as soon as possible if they think they are experiencing worsening of condition.

Compliance information will be captured via eSource (if a patient version is used) or telemedicine. Patient will return unused supply at the EOT visit.

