### **6.2. Prohibited Medications**

Simultaneous participation in other clinical treatment study protocols is not allowed.

Treatment with any antiviral drugs expected to have activity against SARS-CoV-2 are not allowed during therapy with study treatment but may be used as rescue medications. Orlistat results in lowered serum levels of dalcetrapib and is not allowed as this may result in decreased efficacy.

Patients who begin to receive nonstudy rescue antiviral medication for COVID-19 after the start of study treatment will be discontinued from study treatment, they will remain in the study and complete all follow-up assessments.

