## **7.2. Safety and Tolerability Assessments**

### **7.2.1. Adverse Events**

Adverse event definitions, assignment of severity and causality, and procedures for reporting SAEs are detailed in [Appendix 1](#).

The condition of each patient will be monitored from the time of providing informed consent to completion of study participation. Patients will be observed for any signs or symptoms and asked about their condition by open questioning, such as “How have you been feeling since you were last asked?” at each patient contact. Patients will also be encouraged to spontaneously report AEs occurring at any other time during the study.

Any AEs and remedial action required will be recorded in the patient’s source data. The nature, time of onset, duration, and severity will be documented, together with an Investigator’s (or designee’s) opinion of the relationship to study drug.

AEs recorded during the course of the study will be followed up, where possible, until resolution or until the unresolved AEs are judged by the Investigator (or designee) to have stabilized. This will be completed at the Investigator’s (or designee’s) discretion.

For any participants who require hospitalization, if possible, study drug should be continued and an effort made to collect study-related data and conduct End of Study procedures. Every attempt should be made for a visit to be scheduled after discharge from the hospital, providing that the visit is within 28 days of initiation of dosing, or to visit the patient in the hospital, where permitted. In lieu of a study visit, study site staff should obtain equivalent data from hospital records. Pertinent information from hospitalization will be collected, including need for

supplemental oxygenation, mechanical ventilation, days of hospitalization and ventilation, and death.

Serious AEs of worsening COVID-19, with the exception of death, will be considered disease progression and will not be collected for the safety database.

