#### **3.2 Per-Protocol Population**

The Per Protocol (PP) Population will include all participants from the ITT population who have no important study protocol deviations during the study. Because the number of days on study medication is likely to impact the efficacy endpoints, patients who will deviate from the protocol by not taking study medication at least 5 days (as assessed by the difference between date of study treatment last dose – date of study treatment first dose + 1 day) will be excluded. These patients shall be excluded from the PP population prior to database lock.

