#### **6.2.2.2 Censoring**

Severity Symptom Score: For time to resolution, a patient will be censored if the patient has not had the required time point assessment if not due to death. If patient has died or received another antiviral therapy prior to the assessment endpoint, then the patient will be considered as having a moderate or severe COVID-19 symptom for all COVID-19 symptoms and imputed to maximum severity score at the assessment day.

Viral Clearance: For time to viral clearance, a patient will be censored if the patient has not had the required time point assessment.

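### Protocol 4.4.2 stops study drug on admission for worsening COVID-19, 5.5 and 7.2.1 continue it in hospital, and nothing says which prevails

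*Protocol*

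**What the plan says.** Four protocol sections bear on study drug in a hospitalized patient.

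- **4.4.2, Discontinuation of Study Treatment.** In a note under the lack-of-efficacy reason: "Study medication would be discontinued upon worsening of symptoms requiring hospitalization, in such cases patients could receive remdesivir".
- **5.5, Treatment Compliance.** "For patients who are hospitalized, patients will be administered treatment by the site staff during hospitalization". The same paragraph has patients reminded at discharge to keep taking treatment on schedule.
- **7.2.1, Adverse Events.** "For any participants who require hospitalization, if possible, study drug should be continued". The paragraph goes on to list the hospital data to collect, including oxygen use and "mechanical ventilation, days of hospitalization and ventilation, and death".
- **6.2, Prohibited Medications.** "Patients who begin to receive nonstudy rescue antiviral medication for COVID-19 after the start of study treatment will be discontinued from study treatment". Such patients stay in the study for follow-up.

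The synopsis, Protocol 3.1 and SAP 2.1 describe only the follow-up of hospitalized patients, not whether dosing goes on. The SAP does not address dosing in hospital.

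**The concern.** For a patient admitted because COVID-19 symptoms have worsened, one section directs that study drug stop and two direct that it go on. Protocol 7 rules out waivers and calls adherence essential, yet a site that follows one of these sections departs from another. With up to 60 planned sites, the same patient may be handled in opposite ways.

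The first thing at stake is consistent and safe conduct in the sickest participants. The second is what the data mean. Days of exposure and the reason for discontinuation, both tabulated under SAP 6.5.1, would partly reflect which section a site had read. So could membership of the per-protocol set.

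**Working it through.** The plan states no figure on this point, so there is none to reproduce. The check is a comparison of the texts, followed by two short calculations.

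**1. What triggers each rule**

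- 4.4.2: admission for worsening symptoms. Direction: stop. An antiviral is mentioned only as something the patient could then receive.
- 5.5: admission, whatever the reason. Direction: site staff give treatment. No qualifier.
- 7.2.1: admission of any participant. Direction: continue, subject to feasibility.
- 6.2: start of a nonstudy rescue antiviral. Direction: stop. Admission alone is not a trigger.

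**2. Do they meet in the same patient?** Yes, when the admission is for worsening COVID-19. Section 7.2.1 covers every hospitalized participant, and the data it asks for (oxygen, ventilation, death) show that COVID-19 admissions are in view. Section 5.5 makes no exception. Its discharge reminder assumes that dosing may carry on after the stay. An admission for an unrelated reason falls only under 5.5 and 7.2.1, and there the note in 4.4.2 does not conflict with them.

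**3. Is there a tie-breaker?** None of the four sections refers to another on this matter or claims precedence. SAP 1 lets the SAP override the protocol where the two differ, but the SAP says nothing on in-hospital dosing.

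**4. Per-protocol status.** SAP 3.2 excludes "patients who will deviate from the protocol by not taking study medication at least 5 days", counting days as last dose date − first dose date + 1.

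- Last dose on Day 4: 4 − 1 + 1 = 4 days, excluded.
- Last dose on Day 5: 5 − 1 + 1 = 5 days, retained.
- Admitted on Day 3 and stopped that day: 3 − 1 + 1 = 3 days, excluded. The same patient continued to Day 10: 10 − 1 + 1 = 10 days, retained.

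The ambiguity can therefore change status under this rule only for admissions before 5 days on drug. SAP 3.2 also describes these patients as deviating from the protocol. Whether a stop that 4.4.2 itself directs is a deviation depends on which section governs.

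**5. Number of patients.** The documents give no expected hospitalization rate, so 2% to 5% is an assumption.

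- 208 × 0.02 = 4.2
- 208 × 0.05 = 10.4

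That is about 4 to 10 admissions. It is an upper bound for that assumed range, because hospitalization is counted through Day 28 while dosing lasts 10 days, and because only admissions for worsening symptoms meet the conflict.

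**6. Route to the efficacy endpoints.** SAP 3.1 analyzes by assigned treatment. SAP 6.4.3.6 counts patients hospitalized through Day 28 with no condition on dosing, and a patient's first admission comes before any choice to stop or continue. For the symptom endpoints, SAP 6.2.2.2 imputes maximum severity "If patient has died or received another antiviral therapy prior to the assessment endpoint". Neither admission nor stopping study drug triggers that imputation. It follows a stop only when another antiviral is also given.

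**The case against.** The strongest reply is that the specific rule governs the general one. The note in 4.4.2 is confined to worsening symptoms, and 7.2.1 is softened by its feasibility qualifier. A COVID-19 admission could then be a case where continuing is not possible, which leaves 5.5 and 7.2.1 for other admissions. Section 6.2 lends some support, since it too stops study drug when the course of disease leads to another antiviral.

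This reading is not in the text. Section 5.5 has no qualifier, 7.2.1 includes the respiratory outcomes of COVID-19 admissions, and no section states precedence. Section 6.2 does not settle it either, because its trigger is the antiviral and not the admission.

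Parts of the reply do stand. The conflict is confined to admissions for worsening COVID-19 during dosing. The per-protocol set is used only for sensitivity (SAP 6.4), to repeat the primary analysis (SAP 6.4.4). Exposure and reasons for stopping are already to be tabulated by arm, so a stop would be visible, although the table would not show which section the site had followed.

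**Conclusion.** The protocol is internally inconsistent for patients admitted with worsening COVID-19 on Days 1 to 10, and the wording should be corrected. The consequences are for consistent conduct and safety, recorded exposure and reason for discontinuation and, for admissions before 5 days on drug, per-protocol status. At most about 4 to 10 of 208 patients are affected, given the assumed 2% to 5% admission rate.

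A reader might infer more than this, and three such readings are not supported:

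- **That sites will diverge.** The documents show no site behaviour. The text permits divergence, so sites may diverge.
- **That the hospitalization, oxygen and mortality endpoints are compromised.** The hospitalization rate cannot change through this ambiguity. Oxygen use, length of stay and death after admission could in principle depend on whether drug was continued, but the documents give no basis for a size.
- **That the primary analysis is undermined.** The intent-to-treat set requires one dose, not continued dosing. The indirect route through rescue antivirals is limited to a subset of the few patients counted above.

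**What to change.** Reconcile Protocol 4.4.2, 5.5, 7.2.1 and 6.2 into one rule on study drug during hospitalization. State it once and have the other sections refer to it. Section 6.2 must be included, or the admission trigger and the rescue-antiviral trigger will remain unreconciled. No view is taken here on which rule is right; that is for the sponsor.

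Align the recording with the chosen rule: compliance during a hospital stay, last dose date, reason for discontinuation, and whether a stop directed by the protocol counts as a deviation for SAP 3.2.

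The cost is a protocol amendment, which needs IRB/EC approval under Appendix 3. There is no analysis cost.

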#### **4.4.2.1. Liver Injury**

Discontinuation of study treatment for abnormal liver tests should be considered by the Investigator when a patient meets one of the conditions mentioned below or if the Investigator believes that it is in the best interest of the patient.

- Discontinue the study treatment if  $\text{AST/ALT} > 8 \times \text{ULN}$
- Discontinue the study treatment if  $\text{AST/ALT} > 3 \times \text{ULN}$  and serum total bilirubin levels  $> 2 \times \text{ULN}$  (Hys law)
- Discontinue the study treatment if repeat  $\text{AST/ALT} > 5 \times \text{ULN}$

#### **4.4.2.2. Pregnancy**

Female patients who are pregnant or are breastfeeding or who do not agree to use a reliable method of birth control during the study will be permanently discontinued from study drug.

#### **4.4.3. Lost to Follow-up**

A patient will be considered lost to follow-up if he/she repeatedly is unable to be contacted.

The following actions must be taken if a patient repeatedly is unable to be contacted.

- The site must attempt to contact the patient and reschedule the missed visit as soon as possible, counsel the patient on the importance of maintaining the assigned visit schedule, and ascertain whether or not the patient wishes to and/or should continue in the study.
- In cases in which the patient is deemed lost to follow-up, the Investigator or designee must make every effort to regain contact with the patient (where possible, 3 telephone calls and, if necessary, a certified letter to the patient's last known mailing address or local equivalent methods). These contact attempts should be documented in the patient's medical record.
- Should the patient continue to be unreachable, he/she will be considered to have withdrawn from the study with a primary reason of lost to follow-up.

